8.1.3 Investigator Brochure Availability

The current versions of the IBs for the agents will be accessible to site investigators and research staff through the PMB OAOP application. Access to OAOP requires the establishment of a CTEP IAM account and the maintenance of an “active” account status, a “current” password and active person registration status. Questions about IB access may be directed to the PMB IB Coordinator via email.

8.2 Commercial Agent: Azacitidine (NSC # 102816)

Product description:

Chemical Name: 4-amino-1-β-D-ribofuranosyl-s-triazin-2(1*H*)-one

Other Names: 5-azacitidine, 5-aza, azacitidine, Vidaza®

Classification: antimetabolite, DNA hypomethylating agent

CAS Registry Number: 320-67-2

Molecular Formula: C₈H₁₂N₄O₅

M.W.: 244.2

Approximate Solubility: 89 g/L at 25° C in water

Mode of Action: Azacitidine is a pyrimidine nucleoside analog of cytidine. Azacitidine is incorporated into DNA and RNA at high doses and causes direct cytotoxicity as a result of inhibiting DNA and RNA functions. It also inhibits DNA methyltransferase at low doses, therefore causing DNA hypomethylation and subsequent alterations in gene expression.

How Supplied: Azacitidine for injection is supplied as a lyophilized powder in 100 mg single-use vials packaged in cartons of 1 vial (NDC 67211-102-01). It is commercially available. Each vial contains 100 mg of azacitidine and 100 mg of mannitol as a freeze-dried cake or powder.

Solution preparation: As per package insert

Route of administration: Azacitidine may be administered either subcutaneously or intravenously, depending on local institutional practice.

Subcutaneous: The manufacturer recommends equally dividing volumes >4 mL into 2 syringes and injecting into 2 separate sites; however, policies for maximum SubQ administration volume may vary by institution; interpatient variations may also apply. Rotate sites for each injection (thigh, abdomen, or upper arm). Administer subsequent injections at least 1 inch from previous injection sites; do not inject into tender, bruised, red, or hard areas. Allow refrigerated

NCI Protocol #:10200
Version Date: 07/24/2020

suspensions to come to room temperature (up to 30 minutes) prior to administration. Resuspend by inverting the syringe 2 to 3 times and then rolling the syringe between the palms for 30 seconds.

IV: Infuse over 10 to 40 minutes; infusion must be completed within 1 hour of (vial) reconstitution.

Agent Ordering: The agent is commercially available and is considered a standard-of-care drug in this setting.

9. STATISTICAL CONSIDERATIONS

9.1 Study Design/Endpoints

Phase Ib Safety / Tolerability Run In - Primary Endpoint:

- Safety and tolerability will be assessed by evaluating the number of patients out of 6 who experience a dose-limiting toxicity by cycle 1, day 42, using a standard 3+3 design. Two out of 6 events will lead to a dose-reduction or trial discontinuation as described in the analytic plan.

Phase Ib Safety / Tolerability Run In - Primary Endpoint Analytic Plan:

- An incidence of one in six (or fewer) patients experiencing a DLT, as described in section 7, will be considered a safe and tolerable dose.
- Patients who receive at least a full course of therapy will be considered to be evaluable for toxicity/DLT and will not be replaced unless the PI determines that further additional patients at that dose level are required for safety purposes. Patients who experience a DLT prior to completing a full course of therapy will be accounted for in the safety assessment.
- A standard 3+3 design will be used to study patients on an initial pinometostat dose of 54 mg/m²/day continuous IV infusion, in combination with azacitidine at a dose of 75mg/m² daily for 7 days starting on cycle 1, day 1. If two of six experience a DLT within the first 42 days as defined above, the dose of pinometostat will be decreased to 36 mg/m²/day, and it will be combined with azacitidine at a dose of 75mg/m² daily for 7 days in a separate cohort of patients. If two of six experience a DLT within the first 42 days as defined above, the combination will be deemed intolerable and the study will be terminated. If three patients tolerate the combination of standard-dose azacitidine with pinometostat at 54 mg/m²/day, the pinometostat dose may be escalated to 90 mg/m²/day and tested as per standard 3+3 design. Patients who complete cycle 1 would be allowed to stay on single-agent pinometostat through their day 42 evaluation. Patients who achieve count recovery prior to day 42 may be considered for additional combination therapy with azacitidine and may complete up to 6 cycles of combination therapy as described for patients directly enrolled on the phase II protocol.

Phase II Primary Endpoint:

- Response to combination therapy defined as CR, CRi, PR, or MLFS, with or without minimal residual disease (MRD), on bone marrow biopsy as defined by the 2017 European Leukemia Network guidelines will be assessed. Baseline bone marrow biopsy will be performed within 14 days prior to starting therapy, at the end of cycle 1 (day 28 +/- 2 days or time of count recovery), at the end of cycle 3 (+/- 2 days or at the time of count recovery after three cycles of azacitidine administration), at the end of cycle 6 (+/- 2 days or at the time of count recovery after six cycles of azacitidine administration), and / or at the time of therapy discontinuation +/- 3 days. Patients who have stable disease after 4 cycles of combination therapy or progressive disease at any time should be taken off the trial.

Phase II Primary Endpoint Analytic Plan:

- Response rate will be defined as the number of patients who achieve a CR, CRi, PR, or morphologic leukemia-free state (MLFS), with or without MRD, at any time point. Patients will be evaluated through the time of count recovery after 6 cycles of combination therapy.
- A Simon two-stage minimax design will be employed whereby a 20% response rate is considered not promising, a 40% response rate is considered promising, and the probabilities of a type I error (falsely accepting a non-promising therapy) and type II error (falsely rejecting a promising therapy) are set at 0.10 and 0.10, respectively. In the first stage of this design, 19 patients will be accrued. All patients will be followed for a minimum of 24 weeks. If at least 4 patients respond then an additional 17 patients will be accrued to the second stage. At the end of the trial, if 11 or more patients respond out of a total of 36 patients, then this combination will be considered worthy of further investigation. This design yields at least a 0.90 probability of a positive result if the true response rate is at least 40% and yields a 0.90 probability of a negative result if the true response rate is 20%.

9.2 Sample Size/Accrual Rate

Maximum planned sample size is 48 patients, with estimated monthly accrual rate of 3-6 patients among all sites per month.

PLANNED ENROLLMENT REPORT

Racial Categories	Ethnic Categories				Total
	Not Hispanic or Latino		Hispanic or Latino		
	Female	Male	Female	Male	
American Indian/ Alaska Native	0	0	0	0	0
Asian	2	2	0	0	4
Native Hawaiian or Other Pacific Islander	0	0	0	0	0
Black or African American	3	4	0	0	7
White	8	9	2	2	21
More Than One Race	2	2	0	0	4
Total	15	17	2	2	36

9.3 Stratification Factors

N/A

9.4 Analysis of Secondary Endpoints

Phase Ib Safety / Tolerability Run In - Secondary Endpoints:

- Assess safety and tolerability by evaluating the number of patients who experience a dose-limiting toxicity at any time during therapy as defined above.
- H3K79 methylation (assessed by ELISA) on the bone marrow biopsy specimen from prior to therapy initiation and on bone marrow biopsy from day 28 (or time of count recovery)
- Expression levels of HOXA9 and Meis1 (assessed by qPCR), Absolute neutrophil and absolute monocyte count at baseline and day 28
- Evaluate fraction of cells with 11q23 rearrangements before treatment and at day 28
- Evaluate for a rise in absolute neutrophil / absolute monocyte count from baseline

Phase Ib Safety / Tolerability Run In - Secondary Endpoint Analytic Plans:

- Compare quantitative methylation and methylation valence (e.g. if H3K27 has been methylated once, twice, or three times) from baseline and subsequent bone marrow samples using descriptive statistics and graphical displays. A Wilcoxon signed rank test will be used to assess post-treatment differences as compared to baseline. The variability in the assay will be evaluated by collecting a sample at the time of enrollment and at the time of combination therapy initiation, and by running the same sample on the assay multiple times. This variability will be taken into account in determining what percentage change in methylation will be considered significant.
- Compare expression level by qPCR of HOXA9 and Meis1 levels from baseline and subsequent bone marrow samples using descriptive statistics and graphical displays. A Wilcoxon signed rank test will be used to assess post treatment differences as compared to baseline. The variability in the assay will be evaluated by collecting a sample at the time of enrollment and at the time of combination therapy initiation, and by running the same sample on the assay multiple times. This variability will be taken into account in determining what percentage change in methylation will be considered significant.
- Evaluate differentiation by performing a differential on the bone marrow biopsy and peripheral blood samples at baseline and from subsequent time points and assessing percentage of monocytes / neutrophils, bands, and myeloid forms present. Samples will be banked and cytogenetic and FISH analysis of these cells will be performed to evaluate for the presence of MLL-rearrangement in patients who respond to therapy, given funding limitations on performing such an assessment on all patients.

Phase Ib Safety / Tolerability Run In - Exploratory Endpoints:

- Correlative studies will include assessment of incorporation of 5-aza-2'-deoxycytidine incorporation into genomic DNA and the extent of global DNA

methylation and correlation with systemic azacitidine exposure and pharmacodynamics effects.

Phase Ib Exploratory Endpoint Analytic Plans:

- Expect global DNA demethylation / correlation between decitabine systemic PK and decitabine incorporation into genomic DNA; ratio of DAC content/1000 2dC or 5mC content/1000 2dC to express DAC incorporation or global DNA methylation, respectively & methylation changes calculated relative to control 5mC content/1000 2dC ratio. Correlation between systemic azacitidine PK and decitabine incorporation into genomic DNA and other PD measures.

Phase II Secondary Endpoints:

- Assess safety and tolerability by evaluating the number of patients who experience a dose-limiting toxicity at any time during therapy as defined above.
- Assess patient response based on relapsed / refractory or previously untreated status
- H3K79 methylation (assessed by ELISA) on the bone marrow biopsy specimen from prior to therapy initiation and on subsequent bone marrow biopsy samples
- Expression levels of HOXA9 and Meis1 (assessed by qPCR), Absolute neutrophil and absolute monocyte at baseline and on subsequent bone marrow biopsy samples
- Evaluate fraction of cells with 11q23 rearrangements before treatment and on subsequent bone marrow biopsy samples
- Evaluate for a rise in absolute neutrophil / absolute monocyte count at the end of cycle 1 as compared to baseline

Phase II Secondary Endpoint Analytic Plans:

- Patients will be followed for the development of DLTs as described above. All DLTs will be tracked to detect potential toxicities with combination therapy
- Patients will be stratified based on treatment for relapsed / refractory or previously untreated disease. The response of each stratum to combination therapy, defined as CR, CRi, MLFS, or PR, with or without MRD, on bone marrow biopsy as defined by the 2017 European Leukemia Network guidelines, will be described. Kaplan-Meier estimates will be calculated and compared for each stratum, however the small number of patients likely to be enrolled in each stratum will limit the power of this study to detect a difference among them. A report will be generated to look at all patients, all eligible patients who were enrolled, and all evaluable patients.
- Compare quantitative methylation and methylation valence (e.g. if H3K27 has been methylated once, twice, or three times) from baseline and subsequent bone marrow samples using descriptive statistics and graphical displays. A Wilcoxon signed rank test will be used to assess post treatment differences as compared to baseline. The variability in the assay from the phase Ib studies will be taken into account in determining what percentage change in methylation will be considered significant.
- Compare expression level by qPCR of HOXA9 and Meis1 levels from baseline and subsequent bone marrow samples using descriptive statistics and graphical displays. A Wilcoxon signed rank test will be used to assess post treatment differences as compared to baseline. The variability in the assay from the phase Ib studies will be

taken into account in determining what percentage change in methylation will be considered significant.

- Compare 11q23 translocation level as determined by FISH from baseline and subsequent bone marrow samples using descriptive statistics and graphical displays. A Wilcoxon signed rank test will be used to assess post treatment differences as compared to baseline. The variability in the assay from the phase Ib studies will be taken into account in determining what percentage change in translocation detection will be considered significant.
- Evaluate differentiation by performing a differential on the bone marrow biopsy sample and peripheral blood samples at baseline and subsequent bone marrows and assessing percentage of monocytes / neutrophils, bands, and myeloid forms present. Samples will be banked and cytogenetic and FISH analysis of these cells will be performed to evaluate for the presence of MLL-rearrangement in patients who respond to therapy, given funding limitations on performing such an assessment on all patients.

Phase II Exploratory Endpoints:

- Correlative studies will include assessment of incorporation of 5-aza-2'-deoxycytidine into genomic DNA and the extent of global DNA methylation and correlation with systemic azacitidine exposure and pharmacodynamics effects.

Phase II Exploratory Endpoint Analytic Plans:

- Expect global DNA demethylation / correlation between decitabine systemic PK and decitabine incorporation into genomic DNA; ratio of DAC content/1000 2dC or 5mC content/1000 2dC to express DAC incorporation or global DNA methylation, respectively & methylation changes calculated relative to control 5mC content/1000 2dC ratio. Correlation between systemic azacitidine PK and decitabine incorporation into genomic DNA and other PD measures.

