1.2 Secondary Objectives

1.2.1 Phase Ib Safety / Tolerability Run In - Secondary Objectives:

- Perform correlative studies to evaluate for on-target effects, cellular differentiation, and decreased leukemia cell proliferation in these patients
- Correlative studies will include assessment of patterns of histone methylation at H3K79 by ELISA; evaluation of expression of downstream targets of DOT1L-mediated hypermethylation (HOXA9 and Meis1) by qPCR; measurement of myeloid cell differentiation by differential and flow cytometry on bone marrow biopsy samples and peripheral blood samples
- To observe and record anti-tumor activity. Although the clinical benefit of these drug(s) has not yet been established, the intent of offering this treatment is to provide a possible therapeutic benefit, and thus the patient will be carefully monitored for tumor response and symptom relief in addition to safety and tolerability.

1.2.2 Phase II Secondary Objectives:

- Perform correlative studies to evaluate for on-target effects, cellular differentiation, and decreased leukemia cell proliferation in these patients.
- Correlative studies will include assessment of patterns of histone methylation at H3K79 by ELISA; evaluation of expression of downstream targets of DOT1L-mediated hypermethylation (HOXA9 and Meis1) by qPCR; measurement of

NCI Protocol #:10200
Version Date: 07/24/2020

myeloid cell differentiation by differential and flow cytometry on bone marrow biopsy samples and peripheral blood samples

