test and would be solely performed for research purposes as an integrated biomarker. Samples would be viably cryopreserved at each institution and shipped to the study coordinator MSKCC for storage. At the end of the study, the samples would be shipped to DFCI, care of [name] laboratory, and the assay would be batch run on all samples.

We anticipate that pinometostat will induce differentiation of myeloid blasts into more mature myeloid forms, based on previous research on pinometostat. As such, we will prospectively viably cryopreserve bone marrow aspirates in anticipation of flow-sorting blasts and myeloid cells. We will perform flow cytometry to assess for the upregulation of myeloid differentiation markers (such as CD11b) on each myeloid subtype, as well as perform FISH to track the compartmentalization of the MLL rearrangement. We anticipate that MLL rearrangements will be detectable in more mature myeloid cells, e.g. neutrophils, allowing us to evaluate the extent of differentiation.

We will perform these assays on selected samples. CD11B is part of the standard myeloid panel run by the CLIA-certified flow cytometry lab at MSKCC. Bone marrow samples from the above delineated timepoints will be collected and will be a mandatory part of the trial. Bone marrow aspirate samples will be centrifuged and the buffy coat will be viably cryopreserved in DMSO.

Bone marrow will be used to ensure that more blasts can be recovered and myeloid forms at different phases of maturation can be included. While we could consider assays to evaluate for synergy of these two agents, this falls outside the scope of this phase I study – we would need reference evaluations of patient treatment on each agent alone, which is not the goal of this trial. Additionally, *in vitro* assays of synergy have previously been performed in pre-clinical work. Western blots for H3K79 methylation were considered, however we would perform the ELISA first as it provides more throughput with a single assay.

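### Section 9.4 lists a rise in absolute neutrophil/monocyte count as a secondary endpoint but analyses only percentages, which blast clearance alone can raise

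*Combined protocol and SAP*

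**What the plan says.** Section 9.4 puts this endpoint on the absolute scale in both phases. Phase Ib has "Evaluate for a rise in absolute neutrophil / absolute monocyte count from baseline", and phase II has "Evaluate for a rise in absolute neutrophil / absolute monocyte count at the end of cycle 1 as compared to baseline". A second phase II bullet lists "Absolute neutrophil and absolute monocyte at baseline and on subsequent bone marrow biopsy samples", which ties the absolute counts to marrow specimens.

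The analytic plans use another scale. In both phases the bullet on differentiation takes a differential of marrow and blood, "assessing percentage of monocytes / neutrophils, bands, and myeloid forms present". It names no test, no threshold and no denominator that leaves blasts out. Methylation and HOXA9/Meis1 expression, by contrast, each get a Wilcoxon signed rank test against baseline, as does the phase II 11q23 level by FISH.

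Other work on differentiation is planned:

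- The same bullet adds that "cytogenetic and FISH analysis of these cells will be performed to evaluate for the presence of MLL-rearrangement in patients who respond to therapy", and gives limited funding as the reason for the restriction.
- The secondary objectives in Section 1.2 specify "measurement of myeloid cell differentiation by differential and flow cytometry on bone marrow biopsy samples and peripheral blood samples".
- Section 5.1 states "We will perform flow cytometry to assess for the upregulation of myeloid differentiation markers (such as CD11b) on each myeloid subtype", with FISH to follow the rearrangement into mature cells, and then "We will perform these assays on selected samples".

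**The concern.** A listed secondary endpoint has no matching analysis, and the quantity that is assessed in its place leans towards a positive reading. Percentages on a differential sum to 100, so clearing blasts raises the share of every other cell type without one new mature cell. Blast reduction is expected here whether or not pinometostat induces differentiation: every patient receives azacitidine, and Sections 6.1 and 6.4 allow concurrent hydroxyurea. The trial has one arm, so no control group would expose the artefact. What is at stake is the mechanistic conclusion: a rise in mature myeloid forms could be reported as differentiation when it reflects cytoreduction, and the listed endpoint and the written assessment could point in opposite directions in the same patient.

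**Working it through.** The plan states no figure, effect size or test for this endpoint, so there is nothing to reproduce. The documents give no cell counts either; every count below is an assumption chosen to show how the two scales behave.

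**1. Does any bullet analyse absolute counts?** The phase Ib and phase II analytic plans in 9.4 cover DLTs, response by stratum, H3K79 methylation, HOXA9/Meis1 expression, 11q23 level by FISH (phase II) and the differential. None mentions an absolute count. The whole-sample 11q23 analysis does not count mature cells.

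**2. The identity.** Mature % = 100 × mature count / total count. Assume WBC 10, mature cells (neutrophils plus monocytes) 60% of non-blast cells, non-blast cells unchanged, and blasts falling to 5%. With baseline blast fraction b, the mature percentage goes from 60 × (1 − b) to 60 × 0.95 = 57%.

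The last column is the fall in the absolute mature count that would leave the percentage where it started. With q = baseline mature fraction, L = other non-blast cells and B = remaining blasts, the break-even count is q(L + B)/(1 − q). For b = 60%: q = 0.24, L = 1.6, B = 4 × 5/95 = 0.21, so 0.24 × 1.81/0.76 = 0.57, a fall of 76% from 2.4.

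| Baseline blasts | Mature %, before → after | Change in absolute count | Break-even fall |
|---|---|---|---|
| 20% | 48 → 57 | 0 | 30% |
| 40% | 36 → 57 | 0 | 58% |
| 60% | 24 → 57 | 0 | 76% |
| 80% | 12 → 57 | 0 | 90% |

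The fold rises, 0.95/(1 − b), are 1.19, 1.58, 2.38 and 4.75. The share of non-blast cells stays at 60% in every row.

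**3. Opposite answers in one patient.** Start with blasts 6.0, mature 2.4, other 1.6 (mature 24%). Let blasts fall to 0.2 with other cells fixed. If mature cells halve to 1.2, the percentage is 1.2/3.0 = 40%: the percentage rises while the absolute count falls by half.

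**4. Where the rise stops.** From the same start, if mature cells fall to 0.3 (−88%), the percentage is 0.3/2.1 = 14%, below the starting 24%. The percentage rises only if mature cells fall proportionally less than the total count.

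**5. Patients outside the responder FISH.** Halve the blast count with all other cells fixed. The blast percentage becomes 0.5b/(1 − 0.5b): 20% → 11%, 40% → 25%, 60% → 43%, 80% → 67%. Because the total shrinks too, the relative fall in blast percentage is always under one half, so neither the PR requirement of a 50% decrease nor the below-5% blast criterion in Section 12.1.4 is met. The mature percentage still rises: 48 → 53, 36 → 45, 24 → 34 and 12 → 20. (This treats one compartment as standing for both marrow and blood.)

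**6. Group level.** A simulation assumed baseline blasts uniform on 20% to 80%, WBC log-normal with median 8 and log-SD 0.8, a median mature-cell fold change of 1 (log-SD 0.5 or 1.0), other non-blast cells varying with log-SD 0.3, and 2,000 runs per setting. The test was a two-sided 5% signed rank test on raw differences, itself an assumption because 9.4 names none for the differential. The entries are the proportion of trials with a significant rise, percentage scale versus absolute scale.

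| n | Log-SD | Blast count −25% | Blast count −50% |
|---|---|---|---|
| 12 | 0.5 | 19% vs 3% | 68% vs 3% |
| 12 | 1.0 | 11% vs 5% | 29% vs 5% |
| 36 | 0.5 | 61% vs 7% | 99.7% vs 6% |
| 36 | 1.0 | 33% vs 11% | 79% vs 12.5% |

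Here 36 is the phase II maximum and 12 is the remainder of the 48 planned. The absolute-scale figures exceed 2.5% at both sample sizes because log-normal fold changes give right-skewed differences; the absolute analysis is not free of error, only far less affected.

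**The case against.** The strongest reply is that differentiation is analysed as the objective describes it. Section 1.2 specifies the differential and flow cytometry, 9.4 never labels the neutrophil/monocyte bullets as the differentiation endpoint, and the gap is then an omitted analysis of a neighbouring endpoint. That is fair as to labelling. The omission remains, and the percentage differential is still the only written assessment of how many of these cells are present.

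A reader might infer that percentages are the only planned evidence of differentiation. The documents do not support that. FISH in mature cells is the assay best placed to tell differentiation of the clone from blast clearance, and it is planned in responders, where clearance is greatest. But non-responders with partial blast falls are outside the 9.4 FISH, the Section 5.1 work covers selected samples, CD11b flow has no analysis in 9.4, and nothing says how either result would qualify a rise in percentages.

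A reader might also infer that percentages rise whenever blasts fall. They need not, as step 4 shows, and the azacitidine risk list in Section 10.1.2 gives decreased neutrophil count as likely, so stable mature cells cannot be taken for granted.

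Finally, absolute counts are not specific either. Normal marrow recovery raises ANC, CR itself requires ANC above 1000 per microliter, and Section 6.4 allows therapeutic growth factors. This stands, and it shapes the fix. The marrow-sample wording for absolute counts is probably loose drafting: the parallel phase Ib bullet refers to counts at baseline and day 28, and Section 12.1.3 takes ANC from the peripheral CBC.

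**Conclusion.** The concern holds in a limited form. An absolute-scale secondary endpoint in both phases has no analysis, and the percentages assessed in its place can rise through blast clearance alone when mature cells are stable or fall proportionally less than the total count. Under the assumed values the artefact is a 1.19- to 4.75-fold rise when blasts fall to 5%. With 36 patients and halved blasts, a nominally significant rise appears in 79% to 99.7% of simulated trials on percentages, against 6% to 12.5% on absolute counts. These sizes rest wholly on assumed counts and an assumed test.

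It would go too far to say that the trial will wrongly report differentiation. The percentage bullet carries no test or decision rule, and FISH and flow may correct the reading in the patients they cover. The endpoint is a secondary one and does not affect the Simon rule in 9.1 or the toxicity rule in 9.6.

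**What to change.** In Section 9.4, for both phases:

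- Add a paired analysis of peripheral-blood ANC and AMC, baseline to end of cycle 1, by Wilcoxon signed rank test as for the other correlative endpoints, and define what counts as a rise.
- Name the CBC differential, not marrow biopsy samples, as the source of the absolute counts.
- Report differential percentages as a share of non-blast cells, and as supportive only.
- State that a rise in either measure is read as differentiation only alongside the FISH and flow results, since normal marrow recovery also raises ANC; give CD11b flow an analysis; and say which patients lack these assays.

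The cost is wording and a small extra analysis. The calendar in Section 11 already schedules a CBC with differential before treatment, through cycle 1 and on day 1 of cycle 2, so no new sample is needed and the FISH budget is unchanged.

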9.5.2 Evaluation of Response

All patients included in the study must be assessed for response to treatment, even if there are major protocol treatment deviations or if they are ineligible. Each patient will be assigned one of the following categories: 1) complete response, 2) partial response, 3) stable disease, 4) morphologic leukemia-free state, 5) early death from malignant disease, 6) early death from toxicity, 7) early death because of other cause, 8) progressive disease, or 9) unknown (not assessable, insufficient data). [Note: By arbitrary convention, category 9 usually designates the “unknown” status of any type of data in a clinical

database.]

All of the patients who met the eligibility criteria (with the possible exception of those who received no study medication) should be included in the main analysis of the response rate. Patients in response categories 5-9 should be considered to have a treatment failure (disease progression). Thus, an incorrect treatment schedule or drug administration does not result in exclusion from the analysis of the response rate. Precise definitions for categories 4-9 will be protocol specific.

All conclusions should be based on all eligible patients. Subanalyses may then be performed on the basis of a subset of patients, excluding those for whom major protocol deviations have been identified (*e.g.*, early death due to other reasons, early discontinuation of treatment, major protocol violations, etc.). However, these subanalyses may not serve as the basis for drawing conclusions concerning treatment efficacy, and the reasons for excluding patients from the analysis should be clearly reported. The 95% confidence intervals should also be provided.

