12. MEASUREMENT OF EFFECT

Although the clinical benefit of these drugs has not yet been established, the intent of offering this treatment is to provide a possible therapeutic benefit, and thus the patient will be carefully monitored for tumor response and symptom relief in addition to safety and tolerability. Patients with measurable disease will be assessed by standard criteria. For the purposes of this study, patients should be re-evaluated at the end of cycle 1, end of cycle 3, and end of cycle 6.

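### Section 9.4 names Kaplan-Meier as the only way to compare a yes/no response between strata; if early exits are censored, response is overstated

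*Combined protocol and SAP*

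**What the plan says.** Section 9.4 lists this phase II secondary endpoint: "Assess patient response based on relapsed / refractory or previously untreated status". The matching analytic plan stratifies patients by that status. It begins with "The response of each stratum to combination therapy, defined as CR, CRi, MLFS, or PR", with or without MRD, and says this is to be described. The next sentence says "Kaplan-Meier estimates will be calculated and compared for each stratum", and concedes that "the small number of patients likely to be enrolled in each stratum will limit the power" to detect a difference. It gives no event, time origin, censoring rule or test.

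Other sections bear on it:

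- Section 9.1 defines the response rate by counting patients who reach CR, CRi, PR or MLFS at any time point.
- Section 9.5.2 puts all eligible patients, with the possible exception of those never treated, into the main response analysis. It adds: "Patients in response categories 5-9 should be considered to have a treatment failure (disease progression"). Those categories are early deaths, progression and unknown status. It also says "The 95% confidence intervals should also be provided".
- Section 12 says "patients should be re-evaluated at the end of cycle 1, end of cycle 3, and end of cycle 6".
- Section 9.1 removes patients with stable disease after 4 cycles, or with progression at any time.
- Sections 12.1.5 and 12.1.6 define duration of response and progression-free survival (PFS). Neither appears in section 1.2 or in Section 9.

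**The concern.** The endpoint is a proportion, but the only estimator and comparison named for the strata is a time-to-event method. The natural way to apply Kaplan-Meier in that paragraph is to time to first response. Under the usual convention, a patient who dies, progresses or is removed without responding is then censored, that is, treated as if still able to respond later. Section 9.5.2 treats the same patient as a failure.

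Exits before the last assessment are expected by design. A patient removed for stable disease after cycle 4 has left before the end-of-cycle-6 assessment.

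Two things are at stake. The stratum estimates could exceed, and fail to add up to, the overall response rate in section 9.1. The comparison could also be distorted, because the overstatement is larger in the stratum that loses more patients early.

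**Working it through.** **The plan's own response figures.** No figure is stated for the stratum analysis, so the design in section 9.1 is checked first: 19 patients, continue with at least 4 responders, add 17, positive with at least 11 of 36.

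P(positive | p) = sum over x = 4 to 19 of P(Bin(19, p) = x) × P(Bin(17, p) ≥ max(0, 11 − x)).

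- p = 0.20: 0.086, so the probability of a negative result is 0.914.
- p = 0.40: 0.902.

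Both agree with the stated 0.90 levels, and a minimax search returns the same design. The Kaplan-Meier sentence does not enter this calculation.

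**Kaplan-Meier against the proportion.** The documents give no stratum sizes, exit numbers or response timing, so all of these are assumed. Assessments are at the end of cycles 1, 3 and 6.

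- Proportion = responders / all patients in the stratum.
- 1 − KM = 1 − product over assessments of (1 − responders / number at risk). Non-responders who leave drop out of the number at risk.

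| Assumed stratum | Responders at cycles 1, 3, 6 | Censored after cycles 1, 3 | Product | 1 − KM | Proportion | Excess (points) |
|---|---|---|---|---|---|---|
| 18, no early exit | 3, 2, 1 | 0, 0 | (15/18)(13/15)(12/13) = 0.667 | 33.3% | 6/18 = 33.3% | 0 |
| 18, light exit | 3, 2, 1 | 2, 2 | (15/18)(11/13)(8/9) = 0.627 | 37.3% | 33.3% | 4.0 |
| 18, heavier exit | 3, 2, 1 | 5, 4 | (15/18)(8/10)(3/4) = 0.500 | 50.0% | 33.3% | 16.7 |
| 18, heavier exit | 2, 2, 1 | 6, 4 | (16/18)(8/10)(3/4) = 0.533 | 46.7% | 5/18 = 27.8% | 18.9 |
| 12, heavy exit | 2, 1, 1 | 4, 3 | (10/12)(5/6)(1/2) = 0.347 | 65.3% | 4/12 = 33.3% | 31.9 |

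If patients who leave stay in the risk set as never-responders, as section 9.5.2 would suggest, each product collapses to the proportion of non-responders and the excess is zero. The first row shows this algebra.

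**Effect on the comparison.** Assume a 15% chance of response at each assessment and a fixed exit fraction d among non-responders after each one.

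- 1 − KM = 1 − 0.85³ = 38.6%, whatever d is.
- Proportion = 0.15 × [1 + 0.85(1 − d) + (0.85(1 − d))²].
- d = 0: 38.6%. d = 0.2: 32.1%. d = 0.4: 26.6%. d = 0.5: 24.1%.

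So strata with exit fractions of 0.2 and 0.5 differ by 32.1 − 24.1 = 8.0 points in the response rate that section 9.1 defines, yet show identical Kaplan-Meier curves.

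**Precision.** With 6 of 18 responders the exact 95% interval is 13.3% to 59.0%; with 4 of 12 it is 9.9% to 65.1%. For 20% against 40% with an assumed 18 per stratum, power by the normal approximation (two-sided 5%) is Φ[(0.20 − 1.96 × 0.1528)/0.1491] = Φ(−0.667), about 25%.

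**The case against.** The strongest reply is that the paragraph has two sentences, and only the first has response as its subject. The Kaplan-Meier sentence names no endpoint. Section 12.1.6 says PFS will be assessed, section 12.1.5 defines duration of response, Kaplan-Meier is the ordinary method for both, and Section 9 offers no other. On that reading the sentence is incomplete rather than wrong, and deleting it would remove the only method that could serve those endpoints. It can also be said that section 9.5.2 already supplies most of the remedy: eligible patients in the denominator, failures counted as failures, and 95% intervals.

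Much of this stands. A reader might infer that the plan will inflate response by censoring deaths and removals, or that Kaplan-Meier cannot reproduce the rate in section 9.1. The documents support neither. They state no censoring rule, the only rule they give for such patients is failure, and under that rule the two estimates coincide.

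The reply does not rescue the sentence as written. The paragraph is the analytic plan for the response endpoint and names no other comparison of the strata. Neither PFS nor duration of response is linked to it. Duration of response runs from CR or PR, leaving out the CRi and MLFS that section 9.4 counts as response. Section 9.5.2 sets out the main response analysis and does not say how strata are to be compared.

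**Conclusion.** The concern holds in a conditional form. For a yes/no endpoint, section 9.4 names Kaplan-Meier as the only method to estimate and compare the strata, with no time-to-event endpoint in Section 9 to attach it to. That is a mismatch between endpoint and method, beyond missing detail.

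Overstatement follows only if the event is response and early exits are censored. It is then about 4 to 32 percentage points in the assumed early-exit scenarios, and zero if nobody leaves early or exits are kept as failures. These sizes rest on assumed stratum sizes, response timing and exit numbers; they are not predictions for this trial. The Simon decision on 36 patients is untouched. The stratum comparison is secondary, and the plan itself says its power is limited.

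**What to change.** In the section 9.4 paragraph on response by stratum:

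1. Report the response proportion in each stratum with an exact 95% confidence interval. Put all eligible treated patients in the denominator and count categories 5-9 as non-responders; stable disease is already a non-response under section 12.1.4.1.
2. Compare strata by the difference in proportions with an exact or score interval.
3. Restrict Kaplan-Meier to PFS and duration of response as defined in Section 12. State the time origin, censoring rule and any test for each. The censoring rule should take account of section 6.6, where follow-up ends 1 month after removal. State whether the duration-of-response clock is meant to leave out CRi and MLFS.
4. If time to response is reported, use cumulative incidence with death, progression and removal as competing events.

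The cost is a few sentences in section 9.4. No extra patients, visits or data are needed, and the sample size and primary decision rule do not change.
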